3.4 Eligibility Criteria

Eligibility for participation in this study will be based on the inclusion/exclusion criteria. An individual subject may only be included in the study once.

Inclusion Criteria

- 1. Subject has documented Type 1 or Type 2 diabetes mellitus according to the ADA criteria (Appendix B).³³
- 2. Subject has daily pain attributed to symmetrical lower extremity diabetic peripheral neuropathy for at least 6 months prior to screening. Confirmed by score of ≥ 6 on the Toronto Clinical Neuropathy Scoring System.
- 3. Subjects' average lower extremity pain related to diabetic peripheral neuropathy over the preceding 24 hours is ≥4 and <9 based on the 11-point NPRS (0-10) at the Screening Visit.
- 4. Subject age is greater than or equal to 22 years and less than 80 years of age.
- 5. Subject is on stable diabetes treatment which should include medication and/or diet and exercise for at least 3 months prior to Screening.
- 6. Subject has an HbA1c $\leq 10\%$ at Screening or within 3 months of Screening.
- 7. Subject has not changed their analgesic prescriptions in the preceding one month.
- 8. Subject has an ankle-brachial index (ABI) of ≥ 0.8 to ≤ 1.3 . If the subject has incompressible vessels, a toe brachial index of 0.8 to 1.3 is required. These adequate lower extremity studies are with no documented intermittent claudication.
- 9. Subject walks independently with or without assistive devices, and does not require a wheel chair.
- 10. Subject is willing and able to give written informed consent and to comply with all parts of the study protocol.

- 11. Female subjects must be post-menopausal, surgically sterile, abstinent, or, if of childbearing potential, practicing (or agreeing to practice) an effective method of birth control if they are sexually active for the duration of the study. Effective methods of birth control include prescription hormonal contraceptives, intrauterine devices, doublebarrier methods, and/or male partner sterilization.
- 12. Subject can access an internet browser in the home environment or through a smart phone.

Enrollment Visit Inclusion Criteria

- 1. Average diabetic peripheral neuropathic pain intensity (NPRS score) is ≥ 4 and < 9 calculated as the mean of the daily NPRS scores for neuropathic pain in the lower extremities over the 7 days preceding the visit.
- 2. Subject has completed a minimum of 70% of the ePRO assessments during the run-in period.

Exclusion Criteria

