3.12.1 Primary Efficacy Assessment

Pain Intensity (PI)

The primary outcome measure is the absolute change in pain intensity as measured by patient reported numeric pain rating scale (NPRS) evaluations. The NPRS is a validated 11-point numerical rating scale for pain (0=no pain to 10=worst possible pain) collected as patient-reported outcomes in an electronic diary. The NPRS will be scored daily (8am \pm 2 hours) during the 14-day run-in period in order to establish a baseline for purposes of eligibility assessment. During the subsequent 4-month (120-day) treatment period, NPRS will be scored immediately after each morning treatment session (8am \pm 2 hours).

Subjects will be instructed to "Select the one number that best indicates the average intensity of pain you have had over the last 24 hours in your legs".

The primary endpoint is the absolute change from baseline in the NPRS Pain score through Month 4 (Day 120) comparing the PEMF group to the sham group. For purposes of statistical analysis, the baseline NPRS will be the average NPRS during the 7 days preceding the start of treatment with the study device. For subsequent time points, including the primary endpoint at Day 120, NPRS will be calculated as 7-day rolling averages during the treatment period.

During Part B of the protocol (through Month 12 (day 360)), NPRS will be scored immediately after each morning treatment session ($8am \pm 2$ hours) for one week prior to Months 6, 8, 10, and 12. Evaluation of the NPRS during Part B of the protocol will be considered an exploratory endpoint.

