7. STATISTICAL CONSIDERATIONS

The statistical analysis plan for this study will be described in detail in a separate Statistical Analysis Plan (SAP). The initial phase of this study is defined as *Part A* and represents the randomized double-blind portion of the study. Part B is the open-label extension phase where all subjects will receive active therapy.

The primary population for assessing efficacy and safety will be the *Intent to Treat (ITT) Analysis Set*, defined as all subjects who were enrolled into the study and issued a study device.

A secondary analysis of the individual efficacy endpoints will be conducted using the *Per Protocol* (*PP*) *Analysis Set*, defined as all subjects who were enrolled and completed \geq 70% use in treating with the study device.

Subjects will complete a 14-day run in period to obtain an average over the last 7 days in the runin period to obtain the NPRS score for qualification. Once the subject is determined to be eligible, the subject will be enrolled and randomized 1:1 to either an active or inactive sham device and become part of the *ITT and PP sets*.

Subjects in the *ITT and PP sets* will be instructed in the use of the devices for 120 days in the home environment. At months 1, 2, and 3 subjects will return to the clinic to complete PGI and review of adherence to treatment and diary entries. At month 3, subjects will return for completion of the WPAIQ, NeuroQoL and SPP measurements. Subjects will return to the clinic at day 121 for final evaluation and to complete the questionnaires, SPP, QST, and NCS.

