Ho: μ (Change in NPRS score at 4 months / PEMF group) = μ (Change in NPRS score at 4 months / sham group)

Ha: μ (Change in NPRS score at 4 months / PEMF group) $\neq \mu$ (Change in NPRS score at 4 months / sham group)

To compare the absolute change in pain from baseline to 4-months, the intra-patient change will be calculated and serve as the dependent variable in the analysis. The baseline pain score will be introduced in the model as a covariate. Clinical site will be added to the model to assess poolability of the data across sites. Interaction between clinical site and treatment will be evaluated using a type 1 error rate of 10%.

Mixed Models with Repeated Measures (MMRM) comparing results across all time-points will also be performed, adjusted for the baseline value, week, treatment by week interaction and the effect of the patient.

Sub-group analysis will be pre-specified in the SAP and will be performed on subjects with pain scores ≥ 5 as well as subjects with A1C above and below 8.5.

Missing or Incomplete Data

If a patient reports at least 3 days with non-missing pain intensity scores within a particular week, the weekly mean pain intensity score will be derived using the non-missing scores only. This is identical to imputing the missing scores as the mean of the non-missing scores. If the patient reports less than 3 days with non-missing pain intensity scores within a particular week, the weekly mean pain intensity score will be treated as missing data.

Missing weekly mean pain intensity scores will be imputed using multiple missing data and pattern mixture methodology. Sensitivity analyses will be conducted exploring different patterns for missing data. An MMRM will be performed using only observed data without multiple imputation

and an analysis using the change from baseline to the last non-missing weekly mean pain intensity score will also be provided.

The pattern mixture model methodology will be implemented using SAS procedures MI and MIANALYZE. Specifically, the following steps will be followed:

• Intermittent missing data will first be imputed using the Markov Chain Monte Carlo (MCMC) method implemented with the SAS MI procedure, which is appropriate for non-monotonic missing data.

Data for patients who discontinues early will be multiply imputed as follows:

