The Level 3 displays will report the paired results for the change from the baseline through Month 4. For example, if 18 subjects complete the baseline evaluation and 16 subjects complete the Month 4 visit, the difference (Month 4 minus Baseline) will contain 16 subjects.

Supportive individual subject data listings will be sorted and presented by subject number and visit date, if applicable. Listings will also include the number of days relative to the initial study treatment (active or sham).

Specific algorithms are discussed for imputing missing or partially missing dates, if deemed appropriate, under specific data topics. Imputed or derived data will be flagged in the individual subject data listings. Imputed data will not be incorporated into any raw or primary datasets. The imputed data will be retained in the derived / analysis datasets.

The total duration for a subject *on-study* will be calculated as the difference between the date of initial study treatment (active or sham) and the last day of observation plus 1 day. All calculations for defining the duration on-study will follow the algorithm DURATION = [STUDY COMPLETION OR WITHDRAW DATE – INITIAL TREATMENT DATE + 1].

This section details general conventions to be used for the statistical analyses. The following conventions will be applied to all data presentations and analyses.

- Summary statistics will consist of the count and percentage in each level for categorical variables, and the sample size (n) mean, median, standard deviation (SD), minimum, and maximum values for continuous variables.
- All mean and median values will be formatted to one more decimal place than the measured value. Standard deviation values will be formatted to two more decimal places

than the measured value. Minimum and maximum values will be presented with the same number of decimal places as the measured value.

- The number and percentage of responses will be presented in the form XX (XX.X%).
- All probability values will be rounded to four decimal places. All p-values that round to 0.0000 will be presented as '<0.0001' and p-values that round to 1.0000 will be presented as '>0.9999'. P-values <0.05 will be considered to be statistically significant.
- All summary tables will include the analysis population sample size (i.e., number of subjects).

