- Study Day 1 is defined as the day the subject receives their initial exposure to the active study device. All *study days* are determined relative to the day of initial treatment with the study device.
- Baseline values will be defined as those values recorded closest to, but prior to, the first active study treatment.
- Change from baseline will be calculated as follows:
 - Change = Post-baseline value baseline value.
- Date variables will be formatted as DDMMMYYYY for presentation.
- Tables, figures, and listings will be presented in landscape orientation.
- SAS® Version 9.2 or higher will be the statistical software package used for all data analyses.
- All data from this study will be presented in listings. All listings will be sorted by subject number and visit date, as applicable.
- Table and listing numbering will follow ICH guidelines for post-text table and listing numbering.

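### The general baseline rule in SAP 7 and protocol 7.1, applied to the daily NPRS diary, gives a one-day baseline in conflict with the 7-day mean in protocol 3.12.1, and SAP 11 does not restate that mean

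*SAP*

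**What the plan says.** **General rule.** SAP 7 (Analysis Conventions) states: "Baseline values will be defined as those values recorded closest to, but prior to, the first active study treatment". It introduces its list of conventions with: "The following conventions will be applied to all data presentations and analyses". No exception is made for the NPRS. Protocol 7.1 contains the same baseline sentence.

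**NPRS rule.** Protocol 3.12.1 says: "For purposes of statistical analysis, the baseline NPRS will be the average NPRS during the 7 days preceding the start of treatment". Treatment here means use of the assigned device, with no mention of active. For later time points, expressly including the primary endpoint at Day 120, it says "NPRS will be calculated as 7-day rolling averages during the treatment period". Protocol 7.1 adds a minimum for a weekly mean: "If a patient reports at least 3 days with non-missing pain intensity scores within a particular week", the mean is taken over the non-missing scores; with fewer, the weekly mean is missing.

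**SAP 11.** The primary analysis uses the change in NPRS with baseline pain as a covariate. The section defines neither the baseline score nor the Month 4 score, and does not carry over the 3-day minimum.

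**Eligibility averages.** Protocol 3.4 requires a mean NPRS of at least 4 and below 9 "over the 7 days preceding the visit". The Appendix A footnote and SAP 4.1 use the same window. Protocol 7 describes the run-in as serving "to obtain an average over the last 7 days in the runin period to obtain the NPRS score for qualification".

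**Active or sham.** The baseline sentence in both documents, and the Study Day 1 definition in SAP 7, refer to active treatment or the active device. Elsewhere SAP 7 counts days from initial study treatment and specifies that this means active or sham. The protocol's own Study Day 1 definition does not contain the word 'active'.

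**The concern.** A programmer working from the SAP alone could take the last diary score before treatment as baseline and be fully compliant with the stated rule. The primary endpoint would then not be the one in protocol 3.12.1. Baseline NPRS enters four places: the primary change score, its covariate, the responder endpoint (2 points or 30%) and the time-to-response endpoint. Two analysts could derive different values for each and both claim to follow the plan.

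The conflict already exists inside the protocol, between 3.12.1 and 7.1. The SAP carries forward only the general half of it.

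The word 'active' is a second, smaller matter. Sham subjects have no active treatment in Part A. Read literally, those who enter Part B would get a baseline at about Month 4, when they receive an active device, and the others would have none.

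**Working it through.** **1. The plan's own figure.** Inputs from protocol 7.4 and SAP 4.3: mean change 1.79, SD 1.83, placebo effect 40%, two-sided alpha 0.05, power 90%.

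- Difference: 0.6 × 1.79 = 1.074, stated as 1.07.
- n per group = 2 × (1.960 + 1.282)² × 1.83² / 1.07² = 61.5, so 62. The stated figure is reproduced. The exact t-test power at 62 and 1.07 is 89.8%.
- The documents do not say whether 1.83 came from 7-day means or single-day scores, so this point does not alter the 62.

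**2. Cost of a one-day baseline.** These inputs are assumptions, not in the documents: 1.83 is the SD of change between 7-day means; the 7-day baseline SD is 1.2; the baseline to Month 4 correlation is 0.5; daily noise is independent with SD s = 0.5, 1.0 or 1.5; Month 4 remains a 7-day mean.

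- Month 4 SD, y, solves 1.2² + y² − 2 × 0.5 × 1.2 × y = 1.83², giving y = 2.106.
- Baseline to Month 4 covariance = 0.5 × 1.2 × 2.106 = 1.264.
- Residual SD with a 7-day baseline = √(2.106² − 1.264²/1.2²) = 1.824. Power with 121 df is 90.0%.
- A one-day baseline has variance 1.2² + s² − s²/7 = 1.44 + 6s²/7, and the residual SD becomes √(2.106² − 1.264²/(1.44 + 6s²/7)).
- For an unadjusted comparison, which SAP 7.1 says is presented first, the SD is √(1.83² + 6s²/7).

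| Daily SD s | Adjusted residual SD | Adjusted power | Unadjusted SD | Unadjusted power |
|---|---|---|---|---|
| 7-day baseline | 1.824 | 90.0% | 1.83 | 89.8% |
| 0.5 | 1.863 | 88.7% | 1.888 | 87.9% |
| 1.0 | 1.934 | 86.3% | 2.051 | 82.2% |
| 1.5 | 1.991 | 84.4% | 2.297 | 73.0% |

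With baseline SD from 1.0 to 1.5 and correlation from 0.3 to 0.6, the adjusted loss runs from 0.1 points (97.3% to 97.2%) to about 11 points (90.8% to 80.2%).

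**3. Alternative reading of 1.83.** If 1.83 and the baseline SD of 1.2 came from single-day scores with correlation 0.5, and Month 4 is a 7-day mean, adjusted power is 93.3% (7-day baseline) against 91.8% (one-day) at s = 0.5, and 98.3% against 94.4% at s = 0.8. It is above 90% either way.

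**4. Can the protocol 3.12.1 window be empty?** First treatment is on Day 1 (protocol 3.10), so the window is Days −6 to 0. Screening may fall on Day −14 to −17 (4.1), and the diary covers the 14 days after it (4.2). Enrollment requires: "Subject has completed a minimum of 70% of the ePRO assessments during the run-in period". Since 0.70 × 14 = 9.8, at least 10 entries are needed and at most 4 can be missed.

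| Screening day | Diary days in window | Fewest scores possible |
|---|---|---|
| −14 | 7 | 3 |
| −15 | 6 | 2 |
| −16 | 5 | 1 |
| −17 | 4 | 0 |

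The window can be empty only with screening on Day −17 and all four permitted misses on the last four diary days. If the misses are random, that has probability 1/1001, since there are 1001 ways to choose 4 days from 14. A Day 0 entry would remove even this case.

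**The case against.** The best defence is that averaging is plainly intended. The Level 3 table in SAP 7 labels baseline as the enrollment visit. SAP 5 points to Appendix A, where a footnote says the NPRS at that visit is a 7-day average calculated in the EDC system. SAP 4.1 speaks of average baseline pain, and the Kaplan-Meier table in SAP 11 works in weekly means. A specific rule (3.12.1) would normally override a general one. All this stands as evidence of intent. But these are table layout, eligibility text and a table title. None is a derivation rule, and none overrides a sentence that the SAP applies to every analysis and that protocol 7.1 repeats.

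A reader might also infer more than the documents support:

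- **That three baseline windows contradict one another.** Only protocol 3.12.1 defines an analysis baseline. The windows before the enrollment visit and at the end of run-in serve eligibility and need not match it. With screening on Day −15 those two coincide and the analysis window lies one day later.
- **That subjects would lose their baseline under the 3-day minimum.** That minimum is stated for weekly means. Neither document applies it to baseline, and under the SAP's literal rule anyone with a pre-treatment score has a baseline.
- **That the sham arm has no usable baseline, or that the effect would be inflated.** This needs a literal reading that SAP 7 itself contradicts by specifying active or sham.

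**Conclusion.** The point holds as a conflict between stated rules that should be corrected before unblinding. The SAP's only analysis baseline rule permits a one-day NPRS baseline, contrary to protocol 3.12.1, and SAP 11 leaves the Month 4 score and the 3-day minimum unstated.

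The consequence is limited. Either baseline is measured before treatment, so the randomised comparison is not biased. What is lost is precision, consistent responder and time-to-response classification, and a closed analytic choice on the primary endpoint. The central power estimate is a fall of about 1 to 6 points after covariate adjustment, resting wholly on assumed variances and correlation. Unadjusted, the loss could be larger; under the other reading of 1.83, power did not fall below 90% in the cases checked.

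The word 'active' is a minor wording error with clear intent.

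**What to change.** 1. **SAP 11, add:** *NPRS baseline is the mean of the non-missing daily scores in the 7 days before first treatment with the randomised device (protocol 3.12.1). Weekly and Month 4 values are 7-day means and need at least 3 non-missing days (protocol 7.1). The closest-prior-value rule in Section 7 applies only to other measures.* Add the same exception to protocol 7.1.
2. **Baseline sentence in SAP 7 and protocol 7.1:** end it with *first treatment with the randomised study device (active or sham)*. Delete 'active' from the Study Day 1 definition in SAP 7.
3. **Sparse baseline:** do not extend the 3-day minimum to baseline. State that a subject with no score in the 7 days before treatment uses the mean of the last 7 run-in days. With at least 10 of 14 entries, that mean always has at least 3 scores, and all precede treatment, so the rule cannot depend on the arm.

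The cost is a few sentences and word-level edits in two documents, with no new data and no change to the sample size. The downside is that a few subjects with a late enrollment visit or low diary compliance will have a baseline mean based on few days.

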7.1. Adjustments for Covariates

The analyses will be adjusted using the baseline results that are found to differ between the randomized treatment groups to increase the precision of the model; the underlying assumption for inclusion of a covariate or covariates will be examined. Unadjusted analyses will also be conducted and reported as the first set of analyses presented.

Small sites (i.e., sites that have less than 2 patients for any of the treatment arms) will be identified and the following method will be used for combining the data. Data from all small sites will be combined to form a single site in order to obviate non-estimable situations (i.e., at least 2 observations are needed to estimate variance) in the evaluation of the performance of the

Version 3.0 Confidential Page 14 of 31

November 7, 2018

device by site. Once combined, the pooled site will remain as such for all analyses for which a site interaction effect is determined. If the pooled smaller sites represent a single site that has more than twice as many patients as the largest single site, however less than 3 times as many patients, the small sites will be ranked by size and divided into 2 pooled assignments using an alternating sequence (ABABAB). If the pooled smaller sites represent a site that has more than three times as many patients as the largest single site, however less than 4 times as many patients, the small sites will be ranked by size and divided into 3 pooled assignments using an alternating sequence (ABCABCABC). This methodology will be applied, based on the initial pooling of the smaller sites.

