3.12.3 Exploratory Efficacy Assessment

Work Productivity and Activity Impairment Questionnaire: Specific Health Problem

The Work Productivity and Activity Impairment Questionnaire (WPAIQ) is a validated 6 question assessment tool that measures time missed from work, impairment of work and regular activities due to their health problem. Subjects are asked about the effect their diabetic neuropathy has on their ability to work and perform regular activities in the past 7 days. The questionnaire will be completed by the subject at the Enrollment Visit, Month 2, and Month 4.

Biopsy

Two 3 mm punch skin biopsies will be performed at baseline and end of treatment to assess IENFD. At the Enrollment Visit, one biopsy will be obtained at the distal leg, 10 cm above the lateral malleolus on the right leg and a second biopsy will be obtained at the distal thigh, 10 cm above the superior margin of the patella on the lateral right leg. The biopsies will be shipped overnight to the University of Utah Cutaneous Nerve Laboratory. At the end of Part A study visit Month 4 (Day 121), a second set of biopsies will be obtained lateral to the baseline biopsies and shipped overnight to the central lab. Subjects who do not consent to skin biopsies may still be enrolled in the study. Subjects that did not consent to or have biopsies at the Baseline Visit may still have biopsies collected at Month 4 as they enter into the open label extension period. At the end of Part B study visit Month 12 (Day 361), a final set of biopsies will be obtained lateral to the Month 4 biopsies and shipped overnight to the central lab.

NOTE: Skin biopsies will not be performed in subjects receiving anticoagulants. Biopsies may be performed on subjects receiving anti-platelet therapy (i.e. nonsteroidal anti-inflammatory medications, clopidogrel) according to clinical judgment.

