9. BASELINE SUBJECT DATA

9.1. Baseline Demographic Factors

All subjects in the *ITT Population* will be included in Table 14.1.2 entitled *Summary of Baseline Demographics and Subject Characteristics*. The Level 1 table layout will be used to present these results. This table summarizes the subject population with respect to gender, age in years at the time of entry into the study, race, ethnicity, height (cm), weight (lbs), calculated body mass index (BMI), total foot thickness (plantar surface to mid-dorsal surface on the right and left foot) [cm], venous insufficiency classification, diabetes type, HbA1c, foot length (cm), foot width (cm), and shoe size. Data collected using a continuous scale will be summarized using descriptive statistics. Data collected using a categorical scale will be presented using counts and percentages. The supportive data for Table 14.1.2 will be presented in Listing 16.2.4.1 entitled *Subject Demographics and Subject Characteristics*. This listing will be sorted by subject number

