9.2. Screening and Baseline Assessments

The purpose of these assessments is to determine the severity of the disease for each subject. Outcomes may be assessed on baseline disease severity by adding these results as a covariate to the model for analysis. The parameters to be summarized are listed below; the method of summarization will be predicated on the scale used for each parameter (continuous or categorical). Results will be presented using the *Level 1* display for the *ITT Population*.

- Pain Score Assessment (NPRS)
- Toronto Clinical Neuropathy Scoring System (TCNSS)
- Ankle-Brachial Index & Assess Venous Insufficiency
- Quantitative Sensory Test (QST)
- Sural Nerve Conduction Velocity and Amplitude (NCS)
- Measure HbA1c
- Work Productivity and Activity Impairment Questionnaire (WPAIQ)
- Skin Perfusion Pressure (SPP)
- NeuroQoL Questionnaire
- Biopsy measurements

All subjects in the ITT / Safety population will be included in Table 14.1.3 entitled *Summary of Screening and Baseline Assessments* (ITT / Safety population). The supportive data for Table 14.1.3 will be presented in Listing 16.2.4.2 entitled *Screening and Baseline Assessments*. This listing will be sorted by patient number.

Screening assessments will be presented in the following tables:

 Table 14.1.2
 Summary of Baseline Demographics and Subject Characteristics

 Table 14.1.3
 Summary of Screening and Baseline Assessments

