11. EFFICACY EVALUATIONS

The primary endpoint for the study is the change from baseline in the NPRS score at 4 months. The primary hypothesis to be tested is presented below:

Ho: μ (Change in NPRS score at 4 months / PEMF group) = μ (Change in NPRS score at 4 months / sham group)

Ha: μ (Change in NPRS score at 4 months / PEMF group) $\neq \mu$ (Change in NPRS score at 4 months / sham group)

To compare the absolute change in pain from baseline to 4-months, the intra-patient change will be calculated and serve as the dependent variable in the analysis. The baseline pain score will be introduced in the model as a covariate. Clinical site will be added to the model to assess poolability of the data across sites. Interaction between clinical site and treatment will be evaluated using a type 1 error rate of 10%. A Mixed Models with Repeated Measures (MMRM) analysis comparing results across all time-points will also be performed, adjusted for the baseline value, week, treatment by week interaction and the effect of the patient.

The primary efficacy endpoint will be summarized and reported using the Level 3 table design. Results will be presented in Table 14.4.1.1 entitled Summary of the Pain Intensity by Randomized Treatment Assignment and Time (ITT Population)

Listing 16.2.8.1 entitled *Pain Intensity by Randomized Treatment Assignment and Time* will contain all of the recorded information; this listing will be sorted by subject number and relative study day.

A list of additional summary tables is presented in the table below.

Table	Description
14.4.1.1.1	Kaplan-Meier Estimates for the First Week where a Mean Reduction of 2 Points or a 30% Reduction from Baseline in the NPRS is Observed
14.4.1.1.2	Summary of the Pain Intensity Categorized by Success (>=30% reduction from baseline) by Randomized Treatment Assignment and Time
14.4.1.1.3	Summary of the Pain Intensity Categorized by Success (>=2 point reduction from baseline) by Randomized Treatment Assignment and Time
14.4.1.1.4	Summary of the Pain Intensity Categorized by Success (>=2 point reduction or 30% reduction from baseline) by Randomized Treatment Assignment and Time

Table	Description
14.4.1.2	Summary of the NeuroQoL Results by Question, Randomized Treatment Assignment and Time
14.4.1.2.1	Summary of the Efficacy Endpoints by Randomized Treatment Assignment and Time - NeuroQol (Weighted) Domain 1: Pain

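### SAP 7.1 adjusts for baseline results that happen to differ between arms, which does not serve its aim of precision, and the SAP does not fix the primary model in advance, including whether site stays in it

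*SAP*

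**What the plan says.** **Covariates chosen on imbalance.** SAP 7.1: "The analyses will be adjusted using the baseline results that are found to differ between the randomized treatment groups". The sentence gives precision as the reason and ends by saying that the assumption behind including a covariate will be checked. It gives no test, cut-off or list of candidates. The next sentence adds: "Unadjusted analyses will also be conducted and reported as the first set of analyses presented". The protocol has no such rule.

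**The primary comparison.** SAP 11, in line with protocol 7.1: "The baseline pain score will be introduced in the model as a covariate". On site: "Clinical site will be added to the model to assess poolability of the data across sites". The treatment-by-site interaction is tested at 10%. SAP 11 also plans an MMRM adjusted for baseline, week, treatment by week and patient, without site.

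**Site elsewhere.** Protocol 3.6 stratifies randomisation by site. The ANOVA template for efficacy in SAP 13.2 (item 3) contains treatment, center and baseline. The note that opens SAP 13.2 says that not every procedure shown may be needed, and SAP 11 does not refer to the template.

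**Small sites.** Protocol 7.2 pools sites with fewer than 6 patients, wherever a site effect is determined. SAP 7.1 pools sites with fewer than 2 patients in either arm, wherever a site interaction is determined.

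**The concern.** A covariate improves precision when it explains variation in the outcome. Whether it differs between randomised arms is a matter of chance and says nothing about that. A rule that picks covariates on imbalance therefore usually leaves out the useful ones and picks others that only use up information.

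The second issue is which model is primary. SAP 7.1 covers the analyses in general, and SAP 11 describes the primary comparison with fewer terms. A programmer could reasonably fit baseline NPRS alone, baseline NPRS with site, or either one with extra covariates that become known only after by-arm baseline results are seen. These models give different p-values. Site matters most, because a stratified design normally carries its stratification factor into the analysis, and here site is given only a poolability role.

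**Working it through.** **Inputs from the documents.** Two-sided alpha 0.05, 90% power, difference 1.07, SD 1.83, 62 per group (SAP 4.3, protocol 7.4); 1:1 allocation stratified by site (protocol 3.6); up to 20 sites (protocol synopsis).

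**Assumed, because the documents do not give them.** The meaning of differ (p<0.05), the number of candidate covariates and their relation to outcome, R² for baseline NPRS, the site ICC, and equal site sizes.

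**1. The plan's own figure.** n = 2 × (1.960 + 1.282)² × (1.83/1.07)² = 61.5, so 62 per group. The exact t-test has 89.8% power at 62. The stated figure reproduces and is not in dispute.

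**2. What adjustment does to the standard error.** Unadjusted, SE = 1.83 × √(2/62) = 0.329. A covariate with correlation ρ to outcome multiplies this by about √(1 − ρ²); at ρ = 0.5 the result is 0.285. A covariate correlated with treatment (r) also multiplies it by 1/√(1 − r²). At the p = 0.05 boundary with 122 degrees of freedom, t = 1.98 and r² = 3.92/(3.92 + 122) = 0.031, a factor of 1.016. So each covariate the rule picks starts with an SE penalty of at least 1.6%, before any gain from its relation to outcome.

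**3. How often the rule finds a useful covariate.** A given prognostic covariate differs at p<0.05 in about 5% of trials. Simulation: 62 per arm, 10 independent candidates, one prognostic, 8,000 trials per setting, Monte Carlo error about 0.35 points for power and 0.25 for size.

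| ρ | Power, unadjusted | Power, imbalance rule | Power, covariate fixed in advance | Size, imbalance rule |
|---|---|---|---|---|
| 0.3 | 90.4% | 89.9% | 92.6% | 4.7% |
| 0.5 | 89.5% | 89.7% | 95.9% | 4.6% |
| 0.7 | 89.7% | 90.6% | 99.5% | 3.9% |

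Mean SE at ρ = 0.5 is 0.328, 0.329 and 0.285 for the three analyses.

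**4. The rule added to baseline ANCOVA.** Simulation: 16 sites of 8 (64 per arm), baseline R² 0.05, 0.09 or 0.25, ICC 0, 0.05 or 0.10, and either 12 candidates with 2 prognostic or 22 with 6 (R² 0.04 each); 10,000 null and 10,000 alternative trials per setting.
- The rule changes power by -0.7 points (91.3% to 90.6%; 22 candidates, R² 0.05, ICC 0) to +0.1 (97.5% to 97.6%; 22 candidates, R² 0.25, ICC 0.10).
- Fixing the same prognostic covariates in advance gains 1.1 to 1.9 points (two covariates) or 2.2 to 4.8 (six).
- With 22 candidates, R² 0.09 and ICC 0, mean SE is 0.309 for baseline ANCOVA, 0.315 under the rule and 0.272 with the six fixed.
- Size under the rule is 2.7% to 4.8%.

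**5. Site, same simulation.** At ICC 0.10, baseline ANCOVA without site has size 3.3% to 4.0%. With site, size is 4.5% to 5.5% across all settings. Adding site changes power as follows:

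| ICC | Change in power |
|---|---|
| 0 | -0.3 to +0.1 points |
| 0.05 | +0.4 to +0.8 points |
| 0.10 | +0.6 to +1.3 points |

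**6. Pooling rules side by side.** A 5-patient site split 3:2 is pooled under protocol 7.2 (5 is below 6) and kept under SAP 7.1 (both arms have at least 2).

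**The case against.** **SAP 11 is the specific section and already fixes baseline NPRS.** This stands in part: the primary model is not left wholly to the data. But SAP 7.1 uses mandatory wording without exempting the primary analysis, and neither section refers to the other. That SAP 7.1 governs the primary model is one reading, not a settled one.

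**SAP 7.1 says covariate assumptions will be examined.** True, and it might screen out an unsuitable covariate. It does not say that relation to outcome is the criterion, so selection still starts from imbalance.

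**Adjusting for a chance imbalance in a strong predictor helps.** Also true. At ρ = 0.7 the rule gains 90.6 − 89.7 = 0.9 points. The same covariate fixed in advance gains 99.5 − 89.7 = 9.8. Little or no gain on average is the fair statement.

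**The SAP 13.2 template keeps site.** It suggests that this is the intention, but the template is generic and SAP 11 does not invoke it.

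A reader might also infer three stronger points that the documents do not support.

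- *The rule inflates type I error.* Alone it is conservative (2.7% to 4.8%). Inflation needs freedom to cite whichever model succeeds: 5.1% to 6.5% across baseline, baseline plus site and baseline plus imbalance, or 5.8% to 8.1% if the unadjusted result counts too. Nothing in the SAP grants that freedom; it sets only the order in which unadjusted results are presented.
- *Most trials would trigger the rule.* At p<0.05, at least one of 10 independent candidates differs in 1 − 0.95^10 = 40% of trials, and one of 22 in 1 − 0.95^22 = 68%. But SAP 7.1 names no cut-off or list. The general convention ("P-values <0.05 will be considered to be statistically significant") and the baseline lists in SAP 9.1 and 9.2 are not tied to it, the layout for baseline tables has no p-value column, and several listed items overlap, such as height, weight and BMI. SAP 9.2 itself is only permissive: "Outcomes may be assessed on baseline disease severity by adding these results as a covariate to the model for analysis".
- *Selecting biopsy would ruin power.* Biopsy is optional ("Subjects who do not consent to skin biopsies may still be enrolled in the study") and SAP 7.2 does not impute missing values, so adjusting for it would drop patients. Power of 40%, 62% or 76% follows only at assumed uptake of 30%, 50% or 70%, and only if a biopsy measure is selected, about a 5% chance each. It is a tail case.

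**Conclusion.** The concern holds in a limited form. The SAP 7.1 rule does not serve its stated aim: against baseline ANCOVA it moves power by -0.7 to +0.1 points and is mildly conservative, while prognostic covariates fixed in advance gain 1.1 to 4.8 points. SAP 11 does not say whether site, the stratification factor, stays in the primary model; omitting it is conservative and costs about 1 power point at ICC 0.10. The numerical harm is small. The main defects are a covariate rule that fails its own aim and a primary model that is not fixed before the data are seen.

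The sizes depend on the assumed threshold, candidates, R², ICC and site sizes. The text-based points (an imbalance rule stated for all analyses, no statement that site is kept, two pooling rules) need no assumption. The pooling conflict is minor; no effect on the primary estimate has been shown, and it matters here because pooled site would enter the primary model.

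**What to change.** Replace the first paragraph of SAP 7.1 with:

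> The primary analysis is one ANCOVA of change in NPRS at Month 4 with treatment, baseline NPRS and pooled site. Continuous secondary endpoints use the same model with their own baseline where one is collected. No covariate is selected on observed imbalance. Any further prognostic covariates are listed before unblinding and used in a supportive model. Unadjusted results and the MMRM are supportive; site is added to the MMRM.

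The words on collected baselines are needed because PGI has no enrollment assessment in the protocol schedule. Keep the treatment-by-site interaction as a separate test at 10%. State one small-site pooling rule, with one scope, in protocol 7.2 and SAP 7.1.

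**Cost.** SAP wording and a small change to protocol 7.2; the SAP 13.2 template already has these model terms. Site uses up to 20 − 1 = 19 degrees of freedom, fewer after pooling. In the simulation, with 16 − 1 = 15, this cost at most about 0.3 power points when site had no effect, close to Monte Carlo error.
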